SASH is a feasibility study that will provide an intervention to improve opioid use disorder (OUD), quality of life (QOL), and housing outcomes for homeless patients receiving medications for opioid use disorder (MOUD). To achieve these goals, monthly housing vouchers of \$650 that can be used for a broad range of temporary housing included in a list of resources compiled by the study will be used on behalf of the patients in this study. These vouchers will be accompanied by Social Work assistance to find permanent housing which will last the full 12 months of the study. SASH will recruit 8 OUD patients receiving MOUD who are struggling with homelessness, defined as living in an emergency shelter or a place not meant for habitation instead of a fixed, regular, and adequate nighttime residence. This definition is consistent with the one used by the U.S. Department of Housing and Urban Development. The patients will be recruited from the University of Maryland Addiction Treatment Program (ATP), a certified substance use treatment program that provides MOUD and collocates medical care, wellness programs, and research. Patients will be eligible for SASH if they experienced homelessness during at least 15 of the 30 days preceding the dispensing of the first month's stipends. A member of the clinic social work team will start managing the vouchers on behalf of the patients in September 2022. During the first six months of SASH, each monthly voucher of \$650 will be used to find temporary housing included on a list compiled by the study. The type of housing on this list could include rooms in a private dwelling, hotel rooms, or living spaces shared with roommates. In addition to receiving these vouchers, each patient throughout the 12 months of the study will attend regularly scheduled meetings at the ATP with member of the clinic social work team from the University of Maryland Addiction Treatment Program (ATP). During these meetings, the member of the clinic social work team will help house the patient and connect the patient with resources aimed at securing permanent housing, which could include obtaining permanent housing vouchers; connecting the patient with government agencies and services that help individuals struggling with homelessness; or obtaining benefits for which the patient is eligible.

ID: VIEWAE02005CF7000
Name: v2_Lay Summary

HP-00100771

Justification Objective Research Design_V2

Justification, Objective, & Research Design

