This is a feasibility study to determine whether it is achievable to use monthly housing vouchers to secure temporary housing and social work assistance to address housing and other unmet social needs for patients receiving medications for opioid use disorder. All the participants in this study will receive housing vouchers and social work assistance. During the first six months of the study, monthly housing vouchers of \$650 will be managed by member of the clinic social work team on behalf of the participants in the study. The vouchers can be used for a wide range of temporary housing options included on a list compiled by the study. During the twelve months of the study, participants will meet with member of the clinic social work team at the Addiction Treatment Program to address housing and unmet social needs. The meetings will occur at least monthly and will be a requirement for the participants to benefit from the vouchers. The principal Investigator will conduct a chart review of the methadone doses that participants receive in the 3-month period before the study, between Months 3 and 6 of the study, and between Months 9 and 12 of the study. The review of methadone doses will calculate the number of doses participants received and took home with them instead of receiving at the clinic. In addition to a review of methadone doses, the principal investigator will review the results of the urine toxicology tests for the participants in the 3-month period before the start of the study and monthly during the study. Participants will complete two surveys at Day 0, Month 6, and Month 12 of the study: the OUD Checklist, which rates opioid use disorder symptoms based on the DSM-5 criteria, and the SF-36, which measures quality of life. At Months 6 and 12, participants will complete qualitative interviews to determine how the vouchers and social work assistance impacted their financial and social well-being, and whether the SASH intervention was useful in combating homelessness. Data on the methadone doses, results of the urine toxicology tests, surveys, and qualitative interviews will be stored in a password-protected database. The principal investigator will calculate the percentage of days participants are homeless during the 6-month period when vouchers are distributed and at Month 12 of the study. The percentage of days participants are homeless will be calculated from data collected by the member of the clinic social work team. These data will be stored in a password-protected database.

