- * Provide the scientific or scholarly background, rationale, and significance of the research and how it will add to existing knowledge:
The impact of SASH will be significant. Many patients receiving medications for opioid use disorder (MOUD) are homeless and lack the resources to obtain housing, a predicament that negatively impacts their medical and opioid use disorder (OUD) care. By benefiting from the vouchers for temporary housing and receiving assistance from the member of the clinic social work team, patients could experience an improvement in their OUD, which could lead to several downstream health benefits including fewer opioid overdoses, improved psychiatric symptoms, and better social functioning. While previous studies have shown the benefits of providing permanent housing to patients receiving MOUD, none have investigated the benefits of providing temporary housing assistance to these patients. The outcomes of SASH would be written in a manuscript that would be submitted for publication to a high-impact Addiction Medicine Journal. The results of SASH would also be used as pilot data to apply for the Pilot Health Services and Economic Research on the Treatment of Drug, Alcohol, and Tobacco Use Disorders R34 grant. This grant would develop the trial design, study protocols, and data analysis used in an R01 grant that would compare patients receiving the intervention with matched controls. We would submit the R34 grant for the February 16, 2024, application date.

ID: VIEW4E02005EA0C00
Name: v2_Justification, Objective, & Research Design

HP-00100771

Supporting Literature_V2

Supporting Literature

1 * Provide a summary of current literature related to the research: **If you uploaded a separate research protocol document in the 'Research Protocol' page, cite the applicable section and page numbers from that document in the answer box below.**

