The principal Investigator will conduct a chart review of the methadone doses that participants receive in the 3-month period before the study, between Months 3 and 6 of the study, and between Months 9 and 12 of the study. The review of methadone doses will calculate the number of doses participants received and took home with them instead of receiving at the clinic. In addition to a review of methadone doses, the principal investigator will document results of the urine toxicology tests for the participants in the 3-month period before the start of the study and monthly during the study. Participants will complete two surveys at Day 0, Month 6, and Month 12 of the study: the OUD Checklist, which rates opioid use disorder symptoms based on the DSM-5 criteria, and the SF-36, which measures quality of life. At Months 6 and 12, participants will complete qualitative interviews to determine how the vouchers and social work assistance impacted their financial and social well-being, and whether the SASH Intervention was useful in combating homelessness. Data on the methadone doses, urine toxicology tests, surveys, and qualitative interviews will be stored in a password-protected database.

The principal investigator will calculate the percentage of days participants are homeless during the 6-month period when vouchers are distributed and at Month 12 of the study. The percentage of days participants are homeless will be calculated from data collected by the member of the clinic social work team. These data will be stored in a password-protected database. If there are concerns for the well-being of any of the participants in the study, including if a participant expresses thoughts to harm their self or others, then the principal Investigator [name], a board-certified psychiatrist, will be notified to address the situation. If there are medical concerns, one of the study Investigators [name], a Family Medicine physician, will be notified to address the situation. If the situation involves a potentially life-threatening emergency, then the participant will be sent to the Emergency Department.

2 * Describe all procedures already being performed for diagnostic or treatment purposes (If not applicable to the study, enter "N/A"):

All the participants will be currently receiving methadone for opioid use disorder treatment at the Addiction Treatment Program.

3 * Describe the duration of an individual participant's participation in the study:

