Participants will participate in the study for 12 months.

4 * Describe the amount of time it will take to complete the entire study:
The study will take 15 months to complete the study and data analysis.

5 * Describe any additional participant requirements:

Participants will be recruited for the study if they are receiving methadone from the Addiction Treatment Center at the University of Maryland and are struggling with homelessness, which will be defined as living in an emergency shelter or a place not meant for habitation instead of a fixed, regular, and adequate nighttime residence for at least 15 of the 30 days preceding the first month of the study.

HP-00100771

Sample Size and Data Analysis_V2

Sample Size and Data Analysis

If you uploaded a separate research protocol document in the 'Research Protocol' page, cite the applicable section and page numbers from that document in the answer boxes below.

- 1 * Provide the rationale and sample size calculations for the proposed target population:
The study will recruit eight participants. This is a feasibility study, so the results will be used as pilot data to apply for a larger grant.
- 2 * Provide the plan for data analysis. Include in the description the types of comparisons that are planned (e.g., comparison of means, comparison of proportions, regressions, analysis of variance, etc.), which is the primary comparison/analysis, and how the analyses proposed will relate to the primary purposes of the study:
All the participants in this study will receive the intervention. The participants will not be compared with a matched control group. Comparisons of the percentages of missed and take-home methadone doses will be completed in the 3-month period before the study, between Months 3 and 6 of the study, and between Months 9 and 12 of the study. Comparisons will be completed of the results of the urine toxicology tests in the 3-month period before the start of the study and each month during the study. Comparisons will be completed for the OUD Checklist and SF-36 scores at each of the three time points. The analyses will determine how the study interventions impacted outcomes for opioid use disorder treatment, quality of life, and housing.

ID: VIEW4E02000052800
Name: v2_Sample Size and Data Analysis

HP-00100771

Sharing of Results_V2

Sharing of Results

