Participants will undergo an informed consent process, during which participants will be given the opportunity to ask any questions or bring up any concerns about the study. The information from this study will not be given to anyone outside of the study, and it will not be used in the treatment participants receive at the Addiction Treatment Center.

ID: VIEW8068FCA56796D0B

Name: v2_Vulnerable Populations - Economically/Educationally Disadvantaged

HP-00100771

Eligibility_V2

Eligibility

1 * Do you have an existing Eligibility checklist(s) for this study?
 Yes No

1.1 If Yes, upload here. If you need a template, you can download it by clicking **HERE**. The checklists you upload will also be available under the Documents tab of this application.

Name	Created	Modified Date
------	---------	---------------

There are no items to display

1.2 If No, create an eligibility checklist below:

List Inclusion criteria (List each Inclusion Criteria individually, using the ADD button):

Number Criteria

View 1	Participant must be receiving methadone for opioid use disorder treatment at the University of Maryland Addiction Treatment Center.
View 2	Participant must be living in an emergency shelter or a place not meant for habitation instead of a fixed, regular, and adequate nighttime residence for at least 15 of the 30 days preceding the first month of the study.
View 3	Participant expects to continue receiving methadone treatment at the Addiction Treatment Program at the University of Maryland for at least a year.

List exclusion criteria (List each Exclusion Criteria individually, using the ADD button):

Number Criteria

View 1	Participant is unwilling to meet with the member of the clinic social work team at the Addiction Treatment Center for regularly scheduled appointments to address their housing and other unmet social needs.
View 2	Participant expects to have their own housing within the next three months.
View 3	Participant expects to enter an intensive outpatient substance use program that has supportive housing within the next three months.
View 4	Participant has either children or dependents living with them.

After entering the inclusion and exclusion criteria above, click the Save link. CICERO will automatically generate a printable Eligibility Checklist for you to use in your research. To review the checklist, click on the resulting link below. This checklist is also available under the Documents tab of this application.

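### The analysis plan promises to determine impact from one uncontrolled arm of eight, and housing is the one quantitative outcome with no listed comparison and no stated pre-study period

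*Combined protocol and SAP*

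**What the plan says.** Sample Size and Data Analysis, item 2, answers a form prompt that asks for the planned comparisons, "which is the primary comparison/analysis, and how the analyses proposed will relate to the primary purposes of the study". The answer states that everyone receives the intervention and that "The participants will not be compared with a matched control group". It then lists three sets of comparisons: missed and take-home methadone doses, urine toxicology, and scores on the OUD Checklist and SF-36. It closes with: "The analyses will determine how the study interventions impacted outcomes for opioid use disorder treatment, quality of life, and housing".

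Housing is measured elsewhere. Study Procedures, item 1, says: "The principal investigator will calculate the percentage of days participants are homeless during the 6-month period when vouchers are distributed and at Month 12". The research design answer under Justification, Objective, & Research Design says the same. Homelessness before the study appears as inclusion criterion 2 under Eligibility, which requires it "for at least 15 of the 30 days preceding the first month of the study".

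The documents are open about the design. The research design answer says: "This is a feasibility study to determine whether it is achievable to use monthly housing vouchers to secure temporary housing". The significance answer in the same section leaves the controlled comparison to a later "R01 grant that would compare patients receiving the intervention with matched controls". The first answer in that section, however, states a hypothesis that opioid use disorder, quality of life and housing outcomes would improve.

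**The concern.** There are two linked problems in item 2.

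First, its closing sentence promises a causal conclusion. With one arm, no comparator and eight people, the data can show how each person changed. They cannot separate the effect of the intervention from what would have happened anyway.

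Second, housing is what the vouchers act on most directly, yet the text does not set up even a descriptive before-and-after result for it. As written, the only housing contrast available is voucher period against Month 12. That shows whether housing held after the vouchers stopped, not whether it improved from entry.

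The results are meant for a manuscript and as pilot data for further grants. An impact statement the design cannot support, or a housing result without a baseline, would carry into both.

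**Working it through.** **The plan's own figure.** The target is eight participants. No alpha, power, effect size, SD or precision target is given, so there is no calculation to reproduce. The steps below show what eight can deliver.

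**Step 1. Outcomes set side by side** (Study Procedures, item 1; Sample Size and Data Analysis, item 2).

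| Outcome | Stated pre-study value | Later values | Comparison in item 2 |
|---|---|---|---|
| Missed and take-home doses | 3 months before | Months 3–6, Months 9–12 | Yes |
| Urine toxicology | 3 months before | Monthly | Yes |
| OUD Checklist, SF-36 | Day 0 | Months 6 and 12 | Yes |
| Percentage of days homeless | None stated | Voucher period, Month 12 | No |

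Housing is the only row without a stated baseline and without a comparison.

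**Step 2. What the entry threshold says about baseline.** The lowest eligible value is 15/30 = 50% and the highest is 30/30 = 100%. The threshold alone leaves each person's baseline open over a range of 50 percentage points.

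**Step 3. The Month 12 window.** The text does not say which days count. As a constructed example with 30-day months, take someone housed through Month 11 and homeless for all of Month 12:

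- Month 12 alone: 30/30 = 100%.
- The three months used for doses at that stage (Months 9–12): 30/90 = 33%.
- Months 7–12: 30/180 = 17%.

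This is an extreme case, chosen to show that the definition matters.

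**Step 4. Precision of a within-participant change.** The 95% interval half-width, in SDs of the paired differences, is t(0.975, n−1)/√n:

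- n = 8: 2.365/2.828 = 0.84.
- n = 7: 2.447/2.646 = 0.92.
- n = 6: 2.571/2.449 = 1.05.

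These figures assume roughly normal differences. That is doubtful for bounded percentages in eight people, so they are approximate and individual values should be shown beside them.

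**Step 5. Change without any effect.** Entry selects people on high recent homelessness, so some later fall can occur with no effect at all. Two features work against this: exclusion criterion 2 removes those who expect their own housing within three months, and Recruitment, item 1, favours candidates judged likely to stay homeless. They reduce the problem, but without a comparator its size cannot be estimated.

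**Step 6. If feasibility is made primary.** Two-sided exact (Clopper–Pearson) 95% intervals for a count out of eight are 63% to 100% for 8/8 and 35% to 97% for 6/8. For 8/8 the lower limit is 0.025^(1/8) = 0.631.

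**The case against.** The strongest reply is that the plan never hides its design. It calls itself a feasibility study, says there is no control group and defers the controlled comparison to a later grant. It plans no significance test, and the causal claim rests on one verb in one sentence. This is fair, and it makes the first part a matter of rewording. The sentence still states what the analyses are meant to conclude, so it should match the design.

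The second reply is that the missing details may sit in forms that are not shown: the Homeless Days Review Form, the form for review of days homeless, and the recruitment criteria. These may hold both the baseline count and the Month 12 window. That stands, and the finding is limited accordingly to what the text states. Even if the forms hold both, item 2 still lists no housing comparison.

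Some stronger readings are tempting but not supported:

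- *The study has no measure of feasibility.* Days homeless in the voucher period bears directly on whether vouchers secured housing. The Month 6 and 12 interviews also ask whether the intervention was useful against homelessness. What is absent is a designated primary analysis.
- *Feasibility is plainly the primary purpose and item 2 ignores it.* The documents state both a feasibility purpose and an improvement hypothesis, and item 2 does relate to the latter. The form asks for a primary analysis, not for a success threshold.
- *The eligibility window is contradictory.* The Lay Summary counts "at least 15 of the 30 days preceding the dispensing of the first" month's stipends, while Eligibility counts from the first month of the study. But vouchers cover the first six study months and are dispensed at the start of the month, so the two descriptions nearly coincide.

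**Conclusion.** The point holds on two counts. Item 2 promises to determine impact, and one uncontrolled arm of eight can only describe within-participant change. Housing is the only quantitative outcome with no comparison in item 2 and no pre-study period stated in the text, so the plan as written yields no before-and-after housing result.

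The size is as follows. The stated entry rule leaves each baseline anywhere from 50% to 100% of days. A mean paired change would carry a 95% half-width of about 0.84 SD with eight complete pairs, on an assumption of approximate normality that is weak here.

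The absence of a named primary analysis is a lesser matter: the documents give two purposes and rank neither. None of this says that eight is the wrong number for a feasibility study or that a control group is needed now. Nor does it say that housing goes unmeasured. The conclusion on baseline and window rests on the text alone and would soften if the unseen forms already define them.

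**What to change.** 1. In item 2, replace the closing sentence with a statement that the analyses will describe within-participant change in these outcomes. Show individual values and paired differences, label any 95% intervals approximate, and make no causal claim.
2. Record each participant's actual number of homeless days in the 30-day eligibility window, which screening already has to check. If a form captures it, name that form in item 2.
3. Add to item 2 a descriptive comparison of percentage of days homeless before the study, in the voucher period and at Month 12. State which days make up the Month 12 window, and note that selection on prior homelessness may produce some fall without any effect.
4. Optional: say whether the improvement hypothesis or feasibility is primary. If feasibility, report a count out of eight, for example the number placed in temporary housing, with an exact 95% interval. Keep removed participants in the denominator, in line with Withdrawal of Participants, item 3, which retains their data.

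The cost is a more modest stated conclusion, a few sentences in item 2, and one recorded count for each of eight people. No change to design, size or procedures is needed.

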5.1 If Yes, what procedures are in place to assure safety?
 All interviews will be conducted in a private room with only the participant and research staff conducting the patient present. If a participant makes any statement or exhibits any behavior concerning for self-harm, then the principal investigator [name], who is a board-certified psychiatrist, will be notified by the interviewer. If the participant is deemed an acute risk for self-harm, then the study team would ensure the patient goes the Emergency Department for a safety evaluation. If after discussing the situation, the situation is deemed not to require an emergency evaluation, then the team can work with the participant to address any unmet psychiatric needs including referring the participant to outpatient psychiatric treatment, which is available at the 1001 clinic. All data will be stored in a password-protected database.

ID: VIEW4E09460F5EC00
 Name: V2_Surveys/Questionnaires

HP-00100771

Interviews_V2

Interviews

You indicated that this study involves key informant or semi-structured individual interviews.

1 * Are any of the questions likely to cause discomfort in participants or cause harm if their confidentiality were breached? (i.e., Illegal activities)

Yes No

2 * Upload a copy of the interview script or guide that will be used to guide the interviews:

Name

 SASH Qualitative Interview Guide(0.01)

Created

Modified Date

6/21/2023 8:45 AM

6/21/2023 8:45 AM

3 * What is the individual duration of each interview and what is the entire duration of the interviews?
Each interview will take 30 minutes. Given that there are 8 participants in the study and each participant will be interviewed twice, the entire duration of the interviews will be eight hours.

4 * How will the interview responses be recorded and by whom?
The interviews will be recorded on a password-protected computer and stored in a password-protected database.

5 * Do any questions elicit information related to the potential for harm to self or others?
 Yes No

